8.4. Timing of Analyses

A single final analysis for purposes of creating a clinical study report will be performed following final database lock using unblinded treatment data. Other intermediate analyses may occur but will be blinded and will not be used to assess the primary or secondary endpoints for any inference claims.

8.5. Multiple Comparisons/Multiplicity

To control the family-wise type I error rate for multiple tests of the primary and key secondary endpoints, the following statistical testing algorithm will be used. Note that all p-values for key

secondary endpoints may be displayed for descriptive purposes only, but only key secondary endpoints deemed significant from the below testing algorithm may be said to demonstrate statistically significant differences between treatments.

The testing algorithm will consist of 3 “sub-families” of endpoints each with their own testing algorithm. In general, the Hochberg testing algorithm will be employed for all sub-families. The Hochberg procedure is a multi-step, step-up testing procedure. The procedure starts with the largest p-value, which is compared to the largest endpoint-specific critical value (i.e. α). Then, if the first hypothesis test does not show statistical significance, testing proceeds to compare the second-largest p-value to $\alpha/2$. Sequential testing continues in this manner until a p-value for an endpoint is statistically significant at α/m , whereupon that endpoint and all subsequent endpoints (with smaller p-values) are concluded to show statistical significance. In general, the Hochberg procedure is known to control the overall type I error rate when the tests are positively correlated among the endpoints being tested (FDA 2022). This is the case for the endpoints within each sub-family, given the similarity of the endpoints within each group.

1) Clinically-implicated sub-family

- a. A modified Hochberg testing algorithm will be used for all endpoints within this sub-family such that the primary endpoint (NAC TNSS AUC_{0-1hr} at year 3) will be tested first and foremost regardless of its p-value, prior to the testing of the key secondary endpoints within this sub-family.
- b. Given there are 5 endpoints including the primary endpoint in this sub-family (see Table 2: Endpoints with Multiplicity Control below), the largest divisor (m) of α will be 5.
- c. Therefore, the steps are as follows:
 - i. Compare the p-value for the primary endpoint with $\alpha = 0.05$. If the p-value is smaller than 0.05 then the treatment effect of the primary endpoint is considered statistically significant. Otherwise, it is considered *not* significant.
 - ii. Regardless of the primary endpoint outcome, compare the largest p-value of the key secondary endpoints to $\alpha/2 = 0.025$. If the p-value is smaller than 0.025 then the treatment effect of this key secondary endpoint (with the largest p-value) is considered statistically significant. Otherwise, continue to next step:
 - iii. Compare the second largest p-value of the key secondary endpoints to $\alpha/3 = 0.0167$. If the p-value is smaller than 0.0167 then the treatment effect of this key secondary endpoint is considered statistically significant. Otherwise, continue to next step:
 - iv. Continue testing the remaining key secondary endpoints in decreasing p-value order at $\alpha/4$ and $\alpha/5$, until statistical significance is reached or all endpoint tests are exhausted.
 - v. Note that at whatever step statistical significance is reached (could be step i, ii, iii, or after), the Hochberg testing algorithm will deem all untested

endpoints (which will have smaller p-values) to be statistically significant.
Note that it is possible for all key secondary endpoints within this sub-family to be considered not significant, if testing proceeds to the smallest p-value and it is not less than $\alpha/5$.

2) Biomarker sub-family

- a. A traditional Hochberg testing algorithm will be used for all endpoints within this sub-family, starting with the largest p-value of the key secondary endpoints being compared to α , then second largest p-value being compared to $\alpha/2$, and so on. An α of 0.05 will be used for this sub-family, independently of the other sub-families.

3) Survey questionnaire sub-family

- a. A traditional Hochberg testing algorithm will be used for all endpoints within this sub-family, starting with the largest p-value of the key secondary endpoints being compared to α , then second largest p-value being compared to $\alpha/2$, and so on. An α of 0.05 will be used for this sub-family, independently of the other sub-families.

Table 2: Endpoints with Multiplicity Control

1) Clinically-implicated sub-family	2) Biomarker sub-family	3) Survey questionnaire sub-family
Primary endpoint (tested first and foremost):		
a) NAC TNSS AUC _{0-1hr} at year 3, for treatment effect of SLIT/dupilumab arm versus double-placebo arm	N/A	N/A
Key secondary endpoints (in no particular order)*		
b) Peak nasal inspiratory flow (Delta PNIF AUC _{0-1hr}) at year 3 c) Peak TNSS at year 3 d) NAC TNSS AUC _{0-1hr} at year 2 e) NAC TNSS AUC _{0-1hr} at year 2, for treatment effect of SLIT/dupilumab arm versus	a) Size of early intradermal skin test response at year 3 b) Size of late intradermal skin test response at year 3 c) Skin prick test endpoint titration response, as defined by the Provocative Concentration at 5mm (PC5) at year 3	a) Weekly seasonal combined symptom medication scores (CSMS) at year 3 using “in-season” data b) Weekly rhinitis quality of life scores (miniRQLQ) measured in-season at year 3 using “in-season” data

SLIT plus dupilumab placebo arm		c) MRSUI measured in-season at year 3 d) Global Evaluation No. 1 at year 3 e) Global Evaluation No. 2 at year 3
---------------------------------	--	---

*Note: For all key secondary endpoints, unless otherwise stated, the treatment effect being tested is SLIT/dupilumab arm *versus* double-placebo arm.

The following biological arguments support each sub-family being independent enough such that each sub-family will be tested at their own alpha of 0.05:

- The primary and key secondary endpoints within the clinically-implicated sub-family refer to responses after a grass pollen allergen challenge in the target organ. This target organ (i.e. the nose) shares a common lymphatic drainage to the sublingual mucosa, the site of application of grass pollen sublingual tablets.
- The biomarker sub-family refers to responses after a grass pollen allergen challenge in the skin that is remote from the nose and its lymphatic drainage and therefore is likely to have a distinct underlying mechanism.
- The survey questionnaire sub-family refers to participant-recorded outcomes of the severity of their hay fever during natural seasonal exposure to grass pollen, rather than a controlled experimental allergen challenge in either the nose or skin.
- For these reasons the 3 sub-families of endpoints may be regarded as distinct for the statistical analyses.

Secondary and exploratory endpoints detailed in this SAP which are not primary nor key-secondary, as well as time points and pairwise comparisons other than those listed above, may have p-values reported for descriptive purposes only, as a means for hypothesis generation.

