8. GENERAL ANALYSIS AND REPORTING CONSIDERATIONS

The following is a list of general analysis and reporting conventions that will be used:

- Categorical variables will be summarized using counts (n) and percents (%) and will be presented in the form n (%). Percentages will be generally rounded to one decimal place.
- In general, first moment statistics, such as the mean, will be reported at 1 more significant digit than the precision of the data. Second moment statistics, such as standard deviation, will be reported at 2 more significant digits than the precision of the data. Other descriptive statistics related to the shape of the data, such as median and range (min/max), will be reported at the same level of precision as the data is recorded. The level of precision may be modified from this convention for specific displays based on clinical judgement.
- Following SAS[®] default rules, the median will be reported as the average of the two middle numbers if the dataset contains an even number of observations.
- Test statistics including *t* and *z* test statistics will be reported to two decimal places.
- Unless otherwise specified, all statistical tests will be 2-sided using type I error rate = 0.05. Estimates and confidence intervals will be reported to 1 more decimal than the original data. *P*-values will be reported to 3 decimal places. *P*-values less than 0.001 will be displayed as “<0.001”; *p*-values greater than 0.999 will be displayed as “>0.999”. A *p*-value will be reported as 1.000 only if it is exactly 1.000 without rounding.
- No preliminary rounding should be performed; rounding should only occur after analysis. To round, the digit to right of last significant digit will be considered: if < 5 then it will be rounded down, if ≥ 5 then it will be rounded up.
- All analysis will be performed using the SAS System version 9.4.

If departures from these general conventions are present in the specific evaluations section of this SAP, then those conventions will take precedence over these general conventions.

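### SAP 8.5 claims family-wise error control over the primary and key secondary endpoints, but three ungated sub-families at 0.05 each do not provide it

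*SAP*

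**What the plan says.** SAP 8.5 states one aim for the whole set of tests: "To control the family-wise type I error rate for multiple tests of the primary and key secondary endpoints". It attaches a consequence to the result: "only key secondary endpoints deemed significant from the below testing algorithm may be said to demonstrate statistically significant differences between treatments". SAP 9.2 repeats that the key secondaries are alpha-controlled. Neither statement is limited to control inside a sub-family.

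The rules that follow are these:

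- "The testing algorithm will consist of 3 “sub-families” of endpoints each with their own testing algorithm". Table 2 of the SAP lists 5 tests in the clinical sub-family (the primary plus 4), 3 in the biomarker sub-family and 5 in the questionnaire sub-family.
- For the biomarker and questionnaire sub-families: "An α of 0.05 will be used for this sub-family, independently of the other sub-families". Both use an ordinary Hochberg procedure.
- In the clinical sub-family a modified Hochberg applies. Step i tests the primary at 0.05. Step ii, whatever the primary shows, compares the largest of the four secondary p-values with 0.025, and later steps use 0.0167, 0.0125 and 0.01. Step v counts step i among the points at which testing can stop with everything still untested declared significant.
- The separate alphas are defended by biological arguments (nose, skin, natural seasonal exposure) that are said to "support each sub-family being independent enough such that each sub-family will be tested at their own alpha of 0.05".

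SAP 13 declares the multiplicity scheme as a change from Protocol 13.3.4, which leaves secondary p-values unadjusted.

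**The concern.** A family-wise claim covers the chance of any false rejection in the named set. Three blocks that each spend 0.05, with nothing linking them, add up to well over 0.05. Distinctness of the blocks is no defence: for a given error per block, independence gives a larger total than positive correlation between blocks.

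The clinical sub-family has a second problem. Hochberg allows 0.05 only for the largest of all five p-values. Here 0.05 always goes to the primary and the step-up tests on the other four are added on top, so the Hochberg guarantee that the SAP cites does not cover this version.

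At stake is the label on 12 key secondary claims. A skin-test or questionnaire result could be reported as significant under family-wise control, including after a failed primary, when the stated protection does not exist.

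**Working it through.** **Inputs.** From SAP 8.5 and Table 2: 5, 3 and 5 tests, and "each sub-family will be tested at their own alpha of 0.05". From SAP 8: "all statistical tests will be 2-sided using type I error rate = 0.05". The SAP expects positive correlation within a sub-family but gives no value. *Assumption:* correlations of 0 to 0.95 within and 0 to 0.9 between sub-families.

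**The SAP's own thresholds.** 0.05/m for m = 1 to 5 gives 0.05, 0.025, 0.0167, 0.0125 and 0.01. These reproduce.

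**Simplest bound.** Three independent sub-families, each at exactly 5%: 1 - 0.95^3 = 0.1426.

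**Clinical sub-family, independent tests.** The four step-up secondaries have error 0.0394 under the null. With the primary: 1 - 0.95 × (1 - 0.0394) = 0.0874. An unmodified Hochberg on the same five tests gives 0.0490.

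**Simulation of the written algorithm.** 13 two-sided z-tests, no true effects, step ii as written, 1,000,000 runs per setting, rates in percent:

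| Correlation within / between | Four clinical secondaries | Clinical sub-family | Biomarker | Questionnaire | All 13 tests |
|---|---|---|---|---|---|
| 0 / 0 | 3.92 | 8.71 | 4.92 | 4.91 | 17.46 |
| 0.3 / 0 | 3.78 | 8.32 | 4.83 | 4.68 | 16.84 |
| 0.5 / 0 | 3.52 | 7.62 | 4.55 | 4.24 | 15.57 |
| 0.7 / 0 | 3.01 | 6.62 | 4.07 | 3.52 | 13.57 |
| 0.9 / 0 | 2.18 | 5.34 | 3.49 | 2.68 | 11.10 |
| 0.5 / 0.3 | 3.49 | 7.62 | 4.52 | 4.24 | 14.48 |
| 0.7 / 0.3 | 2.99 | 6.62 | 4.09 | 3.56 | 12.87 |
| 0.7 / 0.5 | 3.02 | 6.62 | 4.07 | 3.56 | 11.58 |
| 0.7 / 0.7 | 3.02 | 6.64 | 4.12 | 3.57 | 9.60 |
| 0.9 / 0.7 | 2.20 | 5.39 | 3.47 | 2.66 | 8.46 |
| 0.95 / 0.9 | 1.89 | 5.04 | 3.40 | 2.69 | 6.31 |

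Endpoint-specific assumptions (peak TNSS against TNSS AUC 0.8 to 0.9, other pairs within a sub-family lower, between sub-families 0 to 0.3) give 13.6 to 16.2% overall.

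**Error over the 12 key secondaries alone**, from the table rows with unrelated sub-families:

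- independent: 1 - (1 - 0.0392)(1 - 0.0492)(1 - 0.0491) = 13.1%
- 0.5 within: 1 - (1 - 0.0352)(1 - 0.0455)(1 - 0.0424) = 11.8%
- 0.7 within: 1 - (1 - 0.0301)(1 - 0.0407)(1 - 0.0352) = 10.2%

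Because step ii ignores the primary, the same figures apply when the primary works and no secondary does. Under the global null with independence, a false secondary claim beside a failed primary has probability 0.95 × 0.131 = 12.5%.

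**Step v against step ii.** Step v assumes that untested endpoints have smaller p-values than the one that stopped the testing. That holds among the ordered secondaries but not after step i, because the primary is tested first regardless of rank. Read literally, a significant primary would carry all four secondaries. If the primary had 80% power and the secondaries no effect, they would be declared significant about 80% of the time. Step ii contradicts this reading. Under the global null the two readings give the same error, so the table does not depend on the choice.

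**The case against.** The SAP is open about its scheme: it says more than once that each sub-family has its own 0.05, so a careful reader can see that nothing is split. It adds control where the protocol had none and declares the change. This is a single-site Phase II trial whose primary test keeps its two-sided 0.05. Under step ii, the key secondary error inside each sub-family stays below 5%. All of this stands, and it limits the damage. It does not make the opening claim true, since that claim covers the primary and key secondaries together. Recasting it as control per sub-family would still fail for the clinical one.

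A reader might infer more than the documents support:

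- *That 13 to 18% is the plan's error rate.* No correlations are given. The upper end is independence, and 13% is not a floor. The SAP's own distinctness argument does point to low correlation between sub-families, where the total is larger.
- *That 17.5% is the error of the key secondary claims.* It includes the primary's legitimate 5%; the secondaries alone reach about 13%.
- *That a gate on the primary is required.* Family-wise control does not need one. Allowing a secondary claim after a failed primary is a stated design choice, and an ordinary Hochberg also permits it.

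**Conclusion.** The claim of family-wise control is wrong as written. Under the global null the clinical sub-family runs at 8.7% with independent tests, and at 7.6%, 6.6% and 5.3% with correlations of 0.5, 0.7 and 0.9. All 13 tests run at 17.5% under independence, about 13 to 16% at moderate correlation and about 8 to 12% when correlation is high both within and between sub-families. No setting examined brought the total to 5%; the most extreme (0.95 within, 0.9 between) gave 6.3%. The 12 key secondaries alone run at about 13% under independence and about 10 to 12% at moderate correlation. These sizes depend on assumed correlations and on step ii governing. The direction does not depend on the exact correlation within the range examined. The primary test, and the biomarker and questionnaire sub-families taken singly, stay at or below 5%.

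**What to change.** Correct the statement, in a note to the SAP and in the study report:

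1. Withdraw the claim of overall family-wise control and the argument from biological independence.
2. State that error is controlled at 5% for the primary test and within the biomarker and questionnaire sub-families only, and that the clinical sub-family as a whole and the full set of 13 tests exceed 5%. Give those rates as a range tied to stated correlations, not as fixed numbers.
3. Reconcile step v with step ii so that a significant primary does not automatically carry the four clinical secondaries.

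If overall control is wanted, either of two procedures gives it:

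- An unmodified Hochberg at 0.05/3 in each sub-family: at most 1 - (1 - 0.05/3)^3 = 4.92% under independence. The primary then competes at thresholds from 0.0167 down to 0.0167/5 = 0.0033.
- The primary at 0.05 as gate, then Hochberg at 0.05/3 in each sub-family: 5.0% in simulation under the global null, and 4.2 to 4.9% for the secondaries when only the primary has an effect.

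SAP 8.4 places the final analysis after database lock with unblinded data, and the note at the end of the SAP was written after lock. Changing the decision rule now would be post hoc, so report either procedure as a sensitivity result beside the pre-specified one.

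The correction itself costs only wording. Its price is a less favourable stated error rate and weaker key secondary claims; the gated version also allows none after a failed primary.

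### SAP 8.5 step v wrongly lets the Hochberg carry-over start from the primary test, so its text permits all four key secondary endpoints to be declared significant whatever their p-values

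*SAP*

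**What the plan says.** SAP 8.5 opens with its purpose: "To control the family-wise type I error rate for multiple tests of the primary and key secondary endpoints". It adds that only key secondaries passing the algorithm may be described as showing statistically significant differences.

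In the clinically-implicated sub-family the primary, which is the year-3 TNSS AUC over the first hour, is taken out of order: it "will be tested first and foremost regardless of its p-value, prior to the testing of the key secondary endpoints within this sub-family". The divisor runs up to 5: "Given there are 5 endpoints including the primary endpoint in this sub-family". The steps are:

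- **Step i:** the primary is compared with 0.05.
- **Step ii:** "Regardless of the primary endpoint outcome, compare the largest p-value of the key secondary endpoints to" 0.025.
- **Steps iii and iv:** the remaining secondaries, in decreasing order of p-value, are compared with 0.0167, alpha/4 and alpha/5, stopping at the first success.
- **Step v:** the carry-over rule reads "at whatever step statistical significance is reached (could be step i, ii, iii, or after), the Hochberg testing algorithm will deem all untested". Its remaining words grant significance to whatever has not yet been tested, and a parenthesis asserts that the p-values there will be smaller.

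Table 2 lists the four key secondaries: Delta PNIF AUC at year 3, Peak TNSS at year 3, and TNSS AUC at year 2 for the combination against double-placebo and against SLIT plus dupilumab placebo. The note appended to the SAP after database lock corrects only the AUC formula.

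**The concern.** The Hochberg carry-over is valid because hypotheses are tested from the largest p-value down: once one passes, every untested one has a smaller p-value. Testing the primary first, whatever its rank, removes that property at step i. A primary p-value of 0.04 says nothing about whether Delta PNIF has p = 0.01 or p = 0.90. By naming step i, step v applies the carry-over where its stated justification does not hold.

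Step v also conflicts with step ii. If a significant primary settles the four secondaries, step ii has nothing left to test, although it is to be carried out whatever the primary result.

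What is at stake is which secondary results may be reported as error-controlled successes. These include the only comparison of the combination with SLIT alone that is under multiplicity control.

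**Working it through.** **Inputs.** Two-sided alpha is 0.05 (SAP 8). The sub-family has one primary and four key secondaries (SAP 8.5). The primary has 80% power (Protocol 13.6). The correlation among the five test statistics is an assumption: the SAP says only that it is positive, so 0, 0.3, 0.5 and 0.8 were used (exchangeable normal statistics).

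**The plan's own figures.** Alpha/m for m = 1 to 5 gives 0.05, 0.025, 0.0167, 0.0125 and 0.01, which reproduces the stated 0.025 and 0.0167. The power input is also consistent. With 30 per arm and a placebo mean of 3.81, the detectable reduction is (1.960 + 0.842) × SD × √(2/30) / 3.81. This gives 29.0% for SD 1.53 and 32.8% for SD 1.73, against the stated 29% to 33%.

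**Worked example.** Primary p = 0.04; secondaries 0.90, 0.70, 0.50 and 0.30.

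- Steps ii to iv: 0.90 > 0.025, 0.70 > 0.0167, 0.50 > 0.0125, 0.30 > 0.01. None of the four is significant.
- Step v read literally: testing ends at step i and all four are significant.

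Secondaries of 0.03, 0.02, 0.015 and 0.012 give the same split, 0 against 4.

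**Error rates.** These come from simulation with 1,000,000 trials per setting and two-sided p-values.

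*Primary at 80% power, all four secondaries null:* probability of at least one false key-secondary claim.

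| Correlation | Step v literal | Steps ii to iv |
|---|---|---|
| 0 | 0.808 | 0.040 |
| 0.3 | 0.811 | 0.038 |
| 0.5 | 0.813 | 0.035 |
| 0.8 | 0.813 | 0.027 |

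Hand check at correlation 0: a literal claim occurs if the primary passes or steps ii to iv produce a hit, so 1 − (1 − 0.80)(1 − 0.0396) = 0.808. Under the literal rule all four are falsely claimed with probability 0.80.

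*Global null (primary also null):* probability of any false claim in the sub-family.

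| Correlation | SAP steps, with or without step i in step v | Ordinary Hochberg on all five |
|---|---|---|
| 0 | 0.087 | 0.049 |
| 0.3 | 0.083 | 0.047 |
| 0.5 | 0.076 | 0.042 |
| 0.8 | 0.060 | 0.031 |

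Hand check at correlation 0: 1 − 0.95 × (1 − 0.0394) = 0.087. The excess over 0.05 arises because the primary takes the full 0.05 and the secondaries are then tested regardless. The carry-over from step i does not change this figure.

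**Claiming secondaries only after a significant primary, thresholds unchanged.** Under the global null a false claim now requires the primary to pass, so the sub-family rate is 0.05. With the primary at 80% power, the false key-secondary rate at correlation 0 is 0.80 × 0.0396 = 0.032, and it is lower at higher correlation.

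**The case against.** The strongest defence is that step v is a note and acts only on untested endpoints, whereas step ii is an operative instruction to be followed whatever the primary shows. If step ii is carried out, the secondaries are not left untested after step i. Step v then bites only after a success in steps ii to iv, where its premise about smaller p-values is true. The general description of Hochberg earlier in SAP 8.5 carries over only to endpoints with smaller p-values, and step v ends by contemplating that testing may reach the smallest p-value without success. On this view the mention of step i is a stray phrase.

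Much of this stands. A reader might infer that the plan can only be read as awarding all four secondaries, or that steps ii and v can never be reconciled. The text does not support either, because the reading just described is coherent. A third reading limits the carry-over from step i to secondaries with p-values below the primary's. It gives false key-secondary claims of about 0.029 to 0.051 in the same stress test.

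The 0.81 is also mostly the assumed power of the primary passing straight through, and four exactly null secondaries is a harsh assumption. Peak TNSS uses the same readings as the primary AUC, and Protocol 1.2 cites an approximate 30% on-treatment TNSS reduction in the earlier trial. The figure tests strong error control and does not forecast this trial's result.

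The defence does not remove the problem. Step i is named explicitly, the parenthesis describes the untested endpoints without restricting them, and the closing sentence of step v is compatible with the literal reading when the primary fails. A claim rule with three readings and different outcomes is not fully pre-specified.

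**Conclusion.** Step v is wrong as written in naming step i, and it permits an invalid claim rule alongside a valid reading of the carry-over. With the primary at 80% power, four null secondaries and assumed correlations of 0 to 0.8, the chance of a false key-secondary claim is about 0.81 on the literal reading and 0.03 to 0.04 if steps ii to iv govern. Under the global null the literal carry-over adds nothing. Sub-family error is about 0.06 to 0.087 either way, which is a separate shortfall against the stated aim of family-wise control.

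The defect is confined to the four key secondaries of this sub-family. The primary test and the other two sub-families, which use traditional Hochberg, are unaffected. A reader might also infer that false claims were made. The documents contain no results and do not say which reading was applied, so that inference is not supported.

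**What to change.** 1. **Correct step v.** Delete step i from the list of triggering steps and state that the carry-over applies only among the four key secondaries, after a success in steps ii to iv.
2. **Issue it as a dated erratum,** as was done for the AUC formula, saying which reading was applied to the data.
3. **Deal with the remaining error.** The edit in item 1 alone leaves 0.06 to 0.087 under the global null. Either (a) drop the claim of family-wise control for this sub-family, or (b) claim key secondaries only if the primary is significant, keeping the 0.025 to 0.01 thresholds. Option (b) gives about 0.05 under the global null and roughly 0.01 to 0.03 false key-secondary claims with an effective primary.

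**Cost.** Items 1 and 2 are wording. Option (a) gives up a stated property of the analysis. Option (b) is a design change: it reverses the explicit choice to test secondaries whatever the primary shows, and no key-secondary claim in this sub-family is possible if the primary fails. It can only remove claims relative to steps ii to iv, which matters now that the database is locked. Moving to ordinary Hochberg on the four secondaries after a significant primary (0.05, 0.025, 0.0167, 0.0125) would also control error, but it would loosen the thresholds after lock and is harder to defend.
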